11.3 Study Design

The primary cohort and any biomarker negative expansion cohorts defined below will employ single stage A'Hern designs of N=20 and N=10 respectively. The agent will be deemed worthy of further study in the relevant subset of patients (i.e. biomarker positive in any histology, biomarker positive in a particular histology, etc) if the decision rule is met. Operating characteristics are shown below.

Cohort	N	Decision Rule	Alpha	Power
Primary biomarker positive		≥ 3 responses	10%	90%

Histology-specific biomarker positive expansion cohorts will, by definition, be deemed worthy of further study, since they will have at least 3 responses. The table below shows 90% confidence intervals (Wilson method) for a range of observable response rates.

Cohort Size Observed Response Rate		90% Confidence Interval	
10	30%	13% - 56%	
10	40%	19% - 65%	
10	50%	27% - 73%	

11.3.1 **Primary Cohort**:

APEC1621M will evaluate a primary cohort of 20 mutation-matched ("biomarker positive") evaluable patients of any histology for the primary study aim of determining the objective response rate (CR/PR according to the response criteria in Section 12.3) to the agent. Using an A'Hern design⁵³ with alpha=10%, a sample of N=20 will provide 90% power to detect an improvement in response rate from 5%, if the treatment is ineffective, to 25% if the targeted therapy is sufficiently effective to warrant further study. If there are at least 3 responses out of 20 in the primary cohort, the biomarker/therapy match will be deemed a success.

11.3.2 Histology-Specific Biomarker Positive Expansion Cohorts:

If ≥ 3 patients in the primary cohort with the same histology show signs of objective response (CR/PR according to the response criteria in Section 12.3), a histology-specific biomarker positive expansion cohort will open after the primary cohort is completed to up to 7 evaluable patients for a total sample size of 10 evaluable biomarker positive patients with that histology. This will allow us to estimate more precisely the activity in biomarker positive patients of that histology. See

We will open up to 3 such expansion cohorts for biomarker positive patients (i.e., if 3 histologies have \geq 3 responses, we will open a total of 3 expansion cohorts as described above). Note that this can only happen if the response rate in the primary cohort is at least 45% (9/20) and there cannot be more than 21 additional evaluable patients in total for these expansion cohorts.

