12.3 Response Criteria for Patients with Solid Tumors

See the table in Section 8.0 for the schedule of tumor evaluations. In addition to the scheduled scans, a confirmatory scan should be obtained on the next consecutive cycle following initial documentation of objective response.

As outlined, patients will be assigned to one of the following categories for assessment of response: a) solid tumor (non-CNS) and measurable disease (Section 12.4); b) neuroblastoma with MIBG positive lesions (Section 12.5); c) CNS tumor (Section 12.7); and d) lymphoma/histiocytosis (Section 12.8). Note: Neuroblastoma patients who do not

have MIBG positive lesions should be assessed for response as solid tumor patients with measurable disease.

Response and progression will be evaluated in this study using the revised Response Evaluation Criteria in Solid Tumors (RECIST) guideline (version 1.1) [Eur J Ca 45:228-247, 2009]. Key points are that 5 target lesions are identified and that changes in the largest diameter (unidimensional measurement) of the tumor lesions but the shortest diameter of malignant lymph nodes are used in the RECIST v 1.1 criteria.

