12.5.1 Response Criteria

PRIMARY (SOFT TISSUE) TUMOR RESPONSE¹

RESPONSE	ANATOMICAL IMAGING + MIBG (FDG-PET²) IMAGING
Complete Response (CR)	 < 10 mm residual soft tissue at primary site, AND complete resolution of MIBG or FDG-PET uptake (for MIBG non-avid tumors) at primary site
Partial Response (PR)	 ≥ 30% decrease in longest diameter (LD) of primary site MIBG or FDG-PET uptake at primary site stable, improved or resolved
Progressive Disease (PD)	 > 20% increase in longest diameter taking as reference the smallest sum on study (this includes the baseline sum if that is the smallest on study), AND a minimum absolute increase of 5 mm in longest dimension³
Stable Disease (SD)	Neither sufficient shrinkage for PR nor sufficient increase for PD at the primary site

¹Not for use in assessment of metastatic sites

RESPONSE AT METASTATIC SOFT TISSUE AND BONE SITES

RESPONSE	ANATOMICAL IMAGING + MIBG (FDG-PET¹) IMAGING
Complete Response (CR)	 Resolution of all sites of disease defined as: Non-primary target and non-target lesions measure < 10 mm AND Lymph nodes identified as target lesions decrease to a short axis < 15 mm, AND MIBG uptake or FDG-PET uptake (for MIBG non-avid tumors) of non-primary lesions resolves completely
Partial Response (PR)	• ≥ 30% decrease in sum of diameters² of non-primary target lesions compared to baseline, AND all of the following:

² For ¹²³I-MIBG non-avid tumors

³ A mass that has not met PD measurement criteria but has fluctuating ¹²³I-MIBG avidity will not be considered progressive disease.

	 Non-target lesions may be stable or smaller in size AND No new lesions AND ≥ 50% reduction in MIBG absolute bone score (Relative MIBG bone score ≥ 0.1 to ≤ 0.5) or ≥ 50% reduction in number of FDG-PET avid bone lesions^{3,4}

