Minimal disease (MD)	 Any of the following: Bone marrow with ≤ 5% tumor infiltration and remains > 0-≤ 5% tumor infiltration upon reassessment; or Bone marrow with no tumor infiltration that becomes ≤ 5% tumor infiltration upon reassessment; or Bone marrow with >20% tumor infiltration that has > 0-≤ 5% tumor infiltration upon reassessment.
Stable disease (SD)	Bone marrow with tumor infiltration that remains positive with > 5% tumor infiltration upon reassessment but does not meet CR, MD or PD criteria

¹Immunohistochemistry strongly encouraged

DETERMINATION OF OVERALL RESPONSE

RESPONSE	CRITERIA
Complete Response (CR)	All components meet criteria for CR
Partial Response (PR)	PR in at least one component and all other components are either CR, MD (Bone marrow), PR (Soft tissue or Bone) or Not involved (NI); no component with PD.
Minor Response (MR)	PR or CR in at least one component but at least one other component with SD; no component with PD.
Stable Disease (SD)	SD in one component with no better than SD or NI in any other component; no component with PD.
Progressive Disease (PD)	Any component with PD

NI = Not involved, site not involved at study entry and remains not involved; MD = Minimal Disease, for bone marrow assessment only.

Overall Best Response Assessment

Each patient will be classified according to his "best response" for the purposes of analysis of treatment effect. Best response is determined as outlined in Section 12.8 from a sequence of overall response assessments.

Primary Tumor	Soft Tissue and Bone Metastatic Disease (MIBG or FDG-PET or PET/MR)	Bone Marrow Metastatic Disease	Overall
CR	CR	CR	CR
	CR for one response component with either CR or NI for		CR
CR	CR	MD	PR
CR	PR	CR	PR
CR	PR	MD	PR
CR	PR	NI	PR
CR	NI	MD	PR
PR	CR	CR	PR
PR	CR	NI	PR
PR	CR	MD	PR
PR	PR	CR	PR
PR	PR	NI	PR
PR	PR	MD	PR
PR	NI	CR	PR
PR	NI	NI	PR
PR	NI	MD	PR
NI	CR	MD	PR
NI	PR	CR	PR
NI	PR	MD	PR
CR	CR	SD	MR
CR	PR	SD	MR
CR	SD	CR	MR
CR	SD	MD	MR
CR	SD	SD	MR
CR	SD	NI	MR
CR	NI	SD	MR
PR	CR	SD	MR
PR	PR	SD	MR
PR	SD	CR	MR
PR	SD	MD	MR
PR	SD	SD	MR
PR	SD	NI	MR
PR	NI	SD	MR
SD	CR	CR	MR
SD	CR	MD	MR
SD	CR	SD	MR
SD	CR	NI	MR
SD	PR	CR	MR
SD	PR	MD	MR
SD	PR	SD	MR
SD	PR	NI	MR
SD	SD	CR	
SD SD	SD NI	CR CR	MR MR
NI	CR	SD	MR
NI NI		SD SD	
NI NI	PR SD		MR
		CR	MR
SD	SD	MD MD	SD
NI	SD	MD MD	SD
SD	NI NI	MD MD	SD
NI	NI GD	MD	SD
SD	SD	SD	SD
SD	NI	SD	SD
NI NI	SD	SD	SD
NI	SD	NI	SD
NI	NI	SD	SD
	PD in any one component	nor at study enrollment and no PD for any component	PD Not Evalua

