CR: Complete Response; MD: Minimal Disease; PR: Partial Response; MR: Minor Response; SD: Stable Disease; PD: Progressive disease; NI: not involved; site not involved at study entry and remains not involved

Curie Scoring Summary

[figure not shown]
Гable 1a. Scoring skeletal disease

Regions 1 – 9		
Scoring	MIBG uptake	
0	No MIBG uptake	
1	1 focal site	
2	> 1 focal site	
3	≥ 50% of a region	

Table 1b. Scoring soft tissue disease

Region 10 (Primary soft tissue site)	
Scoring	MIBG uptake
0	No soft tissue uptake
1	1 focal soft tissue site
2	> 1 focal soft tissue site
3	≥ 50% of a region (chest, abdomen)

Region	Site	Curie score
1	Head / Neck	
2	Cervico-Thoracic spine	
3	Ribs / Sternum / Clavicles/ Chest	
4	Lumbar / Sacral spine	
5	Abdomen/Pelvis	
6	Upper Extremity (Proximal)	
7	Upper Extremity (Distal)	
8	Lower Extremity (Proximal)	
9	Lower Extremity (Distal)	
10	Soft Tissue	
TOTAL	Total scores from Regions 1 - 10	

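### Neuroblastoma responder status depends on which passage is read: 12.5.1 text or grid, 12.3 or 12.5 for MIBG-negative tumors, and Table 3 or the grid when marrow is stable

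*Combined protocol and SAP*

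**What the plan says.** Patterns below are written primary / soft-tissue and bone metastases / marrow. MD is minimal marrow disease, NI not involved, MR minor response.

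- **Who counts.** Section 11.4 counts a best response of CR or PR. Section 12.3.1.1 makes every other evaluable patient a non-responder, so MR and SD do not count.
- **12.5.1, text.** Overall CR requires CR in all components. Overall PR requires "PR in at least one component and all other components are either CR, MD (Bone marrow), PR" or NI, with no PD. MR requires a CR or PR component together with an SD component. SD requires an SD component with nothing better than SD or NI elsewhere.
- **12.5.1, grid.** CR/CR/MD, CR/NI/MD and NI/CR/MD are each listed as PR. The middle column is headed "Soft Tissue and Bone Metastatic Disease (MIBG or FDG-PET or PET/MR"), so the grid expects FDG-PET patients.
- **12.3.** Category (b), which leads to 12.5, is limited to neuroblastoma with MIBG-positive lesions. A note says that neuroblastoma patients who do not "have MIBG positive lesions should be assessed for response as solid tumor patients with measurable disease", which means 12.4.
- **12.5, 12.5.1 and 8.1.** Section 12.5 adopts the revised neuroblastoma criteria without that limit. In 12.5.1, CR at the primary needs "complete resolution of MIBG or FDG-PET uptake (for MIBG non-avid tumors) at primary site". Footnote 4-C in 8.1 requires baseline FDG-PET/CT or PET/MR for patients without MIBG-avid tumor.
- **12.4.3, Table 3.** For neuroblastoma with measurable disease, overall PR is given for CT/MRI and MIBG results of PR/PR or CR/CR with any marrow status other than PD.

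**The concern.** The primary endpoint is a count of responders, so each patient needs one classification from one rule. Here the same scans and marrow result can give a responder under one passage and a non-responder under another, and nothing says which passage prevails. The trial is single-arm and the decision rule needs only 3 responses in 20, so a choice made after the scans are known could affect the conclusion. Neuroblastoma is also listed in Appendix VII as a target histology for expansion, and an expansion cohort opens on 3 responses in the same histology.

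**Working it through.** **Design figure first.** Section 11.3.1 states that an A'Hern design "with alpha=10%, a sample of N=20 will provide 90% power" for 5% against 25%, with success at 3 or more responses. Exact binomial:

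- alpha = P(X ≥ 3 | n = 20, p = 0.05) = 0.0755, within the 10% ceiling;
- power = P(X ≥ 3 | n = 20, p = 0.25) = 0.9087.

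Both stated figures are reproduced. Nothing below alters them.

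**Conflict 1: text against grid in 12.5.1.** I classified all 4 × 4 × 4 = 64 non-PD patterns (primary CR/PR/SD/NI, metastatic CR/PR/SD/NI, marrow CR/MD/SD/NI) by both rules. I read the CR line as applying to involved components and set NI/NI/NI aside. Apart from three patterns for which the reproduced grid has no row (see the objection), the rules differ in seven:

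| Pattern | Text | Grid | Responder? |
|---|---|---|---|
| CR/CR/MD, CR/NI/MD, NI/CR/MD | no category | PR | depends on the rule |
| SD/SD/MD, SD/NI/MD, NI/SD/MD, NI/NI/MD | no category | SD | no, either way |

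The first three have no PR component (so not PR by text), no SD component (so neither MR nor SD), and are not CR throughout. Section 12.3.1.1 read with the text alone would make them non-responders.

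**Conflict 2: MIBG-negative neuroblastoma.** Illustrative patient: primary down 35%, primary uptake not worse, FDG-avid bone lesions 4 to 3, no new lesions, no other metastases, marrow not involved, findings confirmed.

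- Under 12.4: 35% ≥ 30%, so target PR. Bone lesions persist without progression, so non-target is non-CR/non-PD. Overall **PR, a responder**.
- Under 12.5.1: primary PR. Avid bone lesions fall by (4 − 3)/4 = 25%, short of the 50% needed for metastatic PR, so that component is SD. PR/SD/NI is **MR, a non-responder**.

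If the 12.3 note governs, patients without MIBG-positive lesions never reach 12.5, and the FDG-PET response rules there have essentially nobody to apply to.

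**Conflict 3: Table 3 against the grid, marrow SD.** Reading CT/MRI as the primary component and MIBG as the metastatic component:

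| Imaging | Table 3 (marrow non-PD) | Grid (marrow SD) |
|---|---|---|
| PR/PR | PR | MR |
| CR/CR | PR | MR |

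Table 3 has a MIBG column, so it cannot be meant only for the MIBG-negative patients whom 12.3 sends to 12.4.

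**Size.** One patient is 1/20 = 5 points of response rate. A single reclassified patient decides the result only when the count is 3 under the looser rule and 2 under the stricter one. The probabilities of those counts are:

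| True rate | P(X = 2) | P(X = 3) |
|---|---|---|
| 25% | 0.067 | 0.134 |
| 5% | 0.189 | 0.060 |

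These are ceilings, because the patient must also have neuroblastoma and one of the affected patterns.

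**The case against.** **The grid fills the gap.** For the three CR-plus-MD patterns the text is silent and the grid is explicit, so a reasonable reader would follow the grid. That is probably the intention, and this conflict is the mildest of the three. It still needs correcting, because the text is presented as the criteria and 12.3.1.1 defaults anyone not CR or PR to non-responder.

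**The 12.3 note is specific and so governs.** This is arguable, but 12.5.1 is just as specific about MIBG non-avid tumors, and footnote 4-C requires the scan that 12.5.1 would use.

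**Few patients are affected.** This stands. The sources in section 2.1.1 show very few HRAS-mutant neuroblastomas: one in a 10,000-case series, and no single-nucleotide variant in a 1,089-case neuroblastoma set. The protocol gives no expected number.

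Some stronger readings are tempting but not supported:

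- *The Curie score is a further conflict, because the form's total is "Total scores from Regions 1 - 10" and includes soft tissue.* The PR criterion and footnote 4 to the metastatic response table both specify bone. The looser definition in 12.5 sits in the paragraph on bone lesions, and no response rule uses the form's total.
- *More patterns conflict, such as NI/PR/NI, which the text calls PR.* This pattern, SD/SD/NI and SD/NI/NI only lack rows in a grid visibly damaged in reproduction, so nothing should rest on them.
- *Nodal metastases down 35% with unchanged FDG-avid bone lesions are MR under 12.5.1.* Nodes and bone form one component there. With no CR or PR elsewhere, the result is SD.
- *Power falls to 88.9%.* P(X ≥ 3 | 19, 0.25) = 0.889 assumes one patient whose response could never count. The conflicts affect only particular patterns.

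**Conclusion.** The point holds for three conflicts: the 12.5.1 text against its grid (three patterns change responder status), 12.3 against 12.5 for MIBG-negative tumors, and Table 3 against the grid when marrow is stable. Each can move a neuroblastoma patient into or out of the primary count. The sample size, the 3-response rule, alpha and power do not change, and few patients are likely to be involved. It should be corrected because each patient is worth 5 points and the decision turns on 3 responses. The conclusion assumes that the three relevant grid rows are reproduced correctly (they are legible) and that Table 3's columns correspond to the grid's components as set out above.

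**What to change.** Settle the wording before any response is reviewed:

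1. **Align the 12.5.1 text with its grid.** CR: every involved component CR. PR: at least one component CR or PR, every other component CR, PR, MD or NI, and overall CR not met. SD: at least one component SD or MD, and none CR, PR or PD. The MR line can stay. These definitions reproduce every legible grid row, including NI/NI/MD.
2. **Name one criteria set for MIBG-negative neuroblastoma.** The documents show that 12.3 and 12.5 must be reconciled, not which should prevail. If 12.5 is chosen, category (b) in 12.3 must be widened as well as the note removed; otherwise these patients still fall under category (a) and 12.4.
3. **Remove Table 3 in 12.4.3, or reconcile it with the grid** for stable marrow.
4. **Optional:** label the Curie form so that the relative score uses the bone regions only, as footnote 4 already says.

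The cost is a protocol wording change. No new assessments are needed and no design figure moves.

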12.6 Response Criteria for Patients with CNS Tumors

12.6.1 Measurable Disease

Any lesion that is at minimum 10 mm in one dimension on standard MRI or CT, for CNS tumors.

12.6.2 Evaluable Disease

Evaluable disease is defined as at least one lesion, with no lesion that can be accurately measured in at least one dimension. Such lesions may be evaluable by nuclear medicine techniques, immunocytochemistry techniques, tumor markers, CSF cytology, or other reliable measures.

12.6.3 Selection of Target and Non-Target Lesions

For most CNS tumors, only one lesion/mass is present and therefore is considered

a "target" for measurement/follow up to assess for tumor progression/response. If multiple measurable lesions are present, up to 5 should be selected as "target" lesions. Target lesions should be selected on the basis of size and suitability for accurate repeated measurements. All other lesions will be followed as non-target lesions. The lower size limit of the target lesion(s) should be at least twice the thickness of the slices showing the tumor to decrease the partial volume effect (e.g., 8 mm lesion for a 4 mm slice).

Any change in size of non-target lesions should be noted, though does not need to be measured.

12.6.4 Response Criteria for Target Lesions

Response criteria are assessed based on the product of the longest diameter and its longest perpendicular diameter. Development of new disease or progression in any established lesions is considered progressive disease, regardless of response in other lesions – e.g., when multiple lesions show opposite responses, the progressive disease takes precedence. Response Criteria for target lesions:

- Complete Response (CR): Disappearance of all target lesions. Off all steroids with stable or improving neurologic examination.
- Partial response (PR): ≥ 50% decrease in the sum of the products of the two perpendicular diameters of all target lesions (up to 5), taking as reference the initial baseline measurements; on a stable or decreasing dose of steroids with a stable or improving neurologic examination.
- Stable Disease (SD): Neither sufficient decrease in the sum of the products of the two perpendicular diameters of all target lesions to qualify for PR, nor sufficient increase in a single target lesion to qualify for PD; on a stable or decreasing dose of steroids with a stable or improving neurologic examination.
- Progressive Disease (PD): 25% or more increase in the sum of the products of the perpendicular diameters of the target lesions, taking as reference the smallest sum of the products observed since the start of treatment, or the appearance of one or more new lesions.

Increasing doses of corticosteroids required to maintain stable neurological status should be strongly considered as a sign of clinical progression unless in the context of recent wean or transient neurologic change due e.g. to radiation effects.

12.6.5 Response Criteria for Non-Target Lesions:

- Complete Response (CR): Disappearance of all non-target lesions.
- Incomplete Response/Stable Disease (IR/SD): The persistence of one or more non-target lesions.
- Progressive Disease (PD): The appearance of one or more new lesions and/or unequivocal progression of existing non-target lesions.

12.6.6 Response criteria for tumor markers (if available):

Tumor markers will be classified simply as being at normal levels or at abnormally high levels.

12.6.7 Overall Response Assessment

The overall response assessment takes into account response in both target and non-target lesions, the appearance of new lesions and normalization of markers (where applicable), according to the criteria described in the table below. The overall response assessment is shown in the last column, and depends on the assessments of target, non-target, marker and new lesions in the preceding columns.

Target Lesions	Non-target Lesions	Markers	New Lesions	Overall Response
CR	CR	Normal	No	CR
CR	IR/SD	Normal	No	PR
CR	CR, IR/SD	Abnormal	No	PR
PR	CR, IR/SD	Any	No	PR
SD	CR, IR/SD	Any	No	SD
PD	Any	Any	Yes or No	PD
Any	PD	Any	Yes or No	PD
Any	Any	Any	Yes	PD

Each patient will be classified according to his "best response" for the purposes of analysis of treatment effect. Best response is determined as outlined in Section 12.9 from a sequence of overall response assessments.

12.7 Response Criteria for Patients with Non- Hodgkin Lymphoma/Histiocytosis

Response and progression will be evaluated in this study using the new international criteria proposed by the revised Response Evaluation Criteria in Pediatric non-Hodgkin Lymphoma Criteria⁵⁵, with modification from the Lugano classification.⁵⁹

12.7.1 Disease Parameters

- 12.7.1.1 Measurable disease: A measurable node must have an LDi (longest diameter) greater than 1.5 cm. A measurable extranodal lesion should have an LDi greater than 1.0 cm. All tumor measurements must be recorded in millimeters (or decimal fractions of centimeters).
- 12.7.1.2 Non-measured disease: All other lesions (including nodal, extranodal, and assessable disease) should be followed as nonmeasured disease (e.g., cutaneous, GI, bone, spleen, liver, kidneys, pleural or pericardial effusions, ascites).
- 12.7.1.3 Target lesions: For patients staged with CT, up to six of the largest target nodes, nodal masses, or other lymphomatous lesions that are measurable in two diameters (longest diameter [LDi] and shortest

diameter) should be identified from different body regions representative of the patient's overall disease burden and include mediastinal and retroperitoneal disease, if involved.

12.7.2 Evaluation of Measurable Disease

Complete Response (CR)

Disappearance of all disease. CT or MRI should be free of residual mass or evidence of new disease. FDG-PET should be negative.

Complete Response Unconfirmed (CRu)

Residual mass is negative by FDG-PET; no new lesions by imaging examination; no new and/or progressive disease elsewhere

Partial Response (PR)

50% decrease in SPD (the sum of the products of the largest diameter and the perpendicular diameter for a tumor mass) on CT or MRI; FDG-PET may be positive (Deauville score or 4 or 5 with reduced lesional uptake compared with baseline); no new and/or PD; morphologic evidence of disease may be present in BM if present at diagnosis; however, there should be 50% reduction in percentage of lymphoma cells.

No Response (Stable Disease)

Neither sufficient shrinkage to qualify for PR nor sufficient increase to qualify for PD, taking as reference the smallest sum diameters while on study.

Progressive disease

For those with > 25% increase in SPD on CT or MRI, Deauville score 4 or 5 on FDG-PET with increase in lesional uptake from baseline, or development of new morphologic evidence of disease in BM

12.7.3 Evaluation of Non-measured Lesions (CT-based response, PET/CT based response not applicable)⁵⁹

Complete Response (CR): Absent non-measured lesions.

Partial response (PR): Absent/normal, regressed, lesions, but no increase.

Stable Disease (SD): No increase consistent with progression

Progressive Disease (PD): New or clear progression of preexisting

non-measured lesions.

